4.0 Methodology

4.1 Study Design

A 3- and 6- month open-label multicentre randomized controlled trial with two parallel groups will be conducted. This study will take place in the outpatient setting of the three hospitals [i.e., Hospital Putrajaya, Hospital Pulau Pinang and Universiti Malaya Medical Center (UMMC)) in Malaysia]. Standard chronic disease treatments will be given to both groups of participants, but the CareAide ® app will be provided for the experimental group during the trial. Both groups will be allocated to 1:1 ratio. Randomization number will be generated by using online number generated programme. Consultants reviewing patients at medical, cardiology, diabetes mellitus and asthma clinics will provide referral and notify independent researchers for eligibility and group assignments. Eligible patients will then be instructed to see pharmacists/researchers at outpatient pharmacies to refill their prescriptions and subsequently enrol in the assigned study group either to receive an intervention with CareAide® or to receive normal clinical care. Information and training on the app will be provided by these researchers to the participants.

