4.2 Participant Recruitment, Eligibility Criteria and Study Procedures

Patients will be recruited at the respective outpatient clinics. At the usual care clinic appointments, patients have their demographics and baseline data of blood pressure, blood sugar, basic blood profiles, asthma control and review of their disease management collected by consultants/researchers. Patients who meet the study criteria will then be instructed to see pharmacists/researchers at outpatient pharmacy to refill their medications. The pharmacists/researchers will screen patients' inclusion and exclusion criteria for this study and will explain that they may or may not be selected for the study and if they agree, proceed to provide written informed consent. The adherence data from the screening will be collected to gauge the general adherence rate in these group of patients. An independent researcher, who is not involved in the intervention and control groups, will use the random number function in Excel to generate randomisation sequences. The random numbers will be placed in opaque envelopes, which subsequently will be opened by pharmacists/researchers at the outpatient pharmacies. Participants and pharmacists/researchers are unblinded to group assignment and are aware of the intervention, but the study hypotheses are not disclosed to the participants. The assessor and statisticians are blinded to participant allocation. The study will be evaluating usual care compared with usual care plus pharmacist-driven patient-specific adherence interventions - CareAide® medication adherence digital application. Usual care provided by these hospitals comprises clinic appointments every 3 to 6 months.

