4.4.1.1 Primary outcome

Medication adherence: CareAide® effectiveness is measured with a medication adherence tool at baseline and follow-up time periods at 3 months and 6 months using Morisky Medication Adherence Scale-8 (MMAS-8) and proportion of days covered (PDC). The primary outcome of the study is medication adherence, which is assessed using the 8-item Morisky Medication Adherence Scale (MMAS-8) and the Proportion of Days Covered (PDC) method. Measurements are taken at baseline and at two additional time points, with a 3-month interval following the intervention. MMAS-8 is a licensed validated questionnaire to assess medication adherence, where a higher score represents higher medication adherence and vice versa. Comprising of 8 items, the score ranges from 0 to 8, where a higher score represents a higher medication adherence. The internal consistency (Cronbach's alpha) of MMAS-8 is 0.83 along with a sensitivity of 93% and a specificity of 57%. The PDC method utilises pharmacy refill records (Raebel et al., 2013). The PDC can be calculated as below (Hess et al., 2006; Raebel et al., 2013; Pednekar et al., 2019):

$Nm/Nd \times 100\%$

Where N_m denotes the number of days covered by the medication while N_d meant the number of days in the study period. The patients are considered to be adherent if their PDC scores are ≥ 0.8 or 80% (Karve et al., 2009). The prescription refill data was extracted from outpatient/hospital database.

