Indirect medical or patient out-of-pocket cost such as transportation costs, productivity losses, caregiver costs and waiting time in outpatient visit will be collected with the used of cost questionnaires to the participants. Patients will be requested to report the resource utilization over the past 3 months during the first time after recruitment(baseline) and after every 3 months (at 3 and 6 months). Transportation costs included parking fees. Patient time costs will be calculated based on waiting time in outpatient visit with the wages per hour of patient. Rate of wages per hour will be estimated based on patient's reported income per hour. Productivity losses will not be accounted for patients who are retired and jobless. This economic cost will help to evaluate the economic impact of CareAide from patients' perspective. All costs will be valued in Malaysia Ringgit (MYR).

v. Health-related quality of life (HRQoL) of patients

The overall health state and quality of life will be collected with the EuroQol-5D (EQ-5D-5L) and Short Form 36 Health Survey (SF-36) questionnaires to determine quality-adjusted life years (QALYS) over 3- and 6- months follow-up time. This study will use the EQ-5D-5L and SF-36 surveys to assess the HRQoL of chronic disease patients. The EQ-5D-5L instrument of the EuroQol is a validated tool to measure the health status of various groups in various diseases. This tool composed of five dimensions: mobility, self-care, usual activities, pain/discomfort and anxiety/ depression (Lins et. al., 2016). Another questionnaire SF-36 is a self-reported measure of health with 36 items which cover eight domains of health. The eight domains including vitality, mental health, physical functioning, bodily pain, general health perceptions, physical role functioning, emotional role functioning and social role functioning (Lins et al., 2016). Both tools consist of questionnaires whereas EQ-5D-5L consists of additional visual analogue scale. These tools will be conducted via face-to face or phone interview to assess the health status of respondents.

Trained research personnel will explain the purpose of the study and obtain consent of the participants before distributing or administering the questionnaires. Participants will then be distributed with questionnaires. EQ-5D-5L and SF-36 have different languages versions of the validated phone interview or face-to face questionnaires included English, Malay, Tamil and

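### Blinding an unnamed assessor does not protect MMAS-8, a self-reported co-primary measure tested on its own, from a reporting shift by participants who know their arm

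*Combined protocol and SAP*

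**What the plan says.** Section 4.1 describes the trial as open-label: "A 3- and 6- month open-label multicentre randomized controlled trial with two parallel groups will be conducted". Section 4.2 says "Participants and pharmacists/researchers are unblinded to group assignment and are aware of the intervention, but the study hypotheses are not disclosed to the participants", and then "The assessor and statisticians are blinded to participant allocation". Neither section says who the assessor is or which measurements that person makes.

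Section 4.4.1.1 defines the primary outcome as medication adherence, "which is assessed using the 8-item Morisky Medication Adherence Scale (MMAS-8) and the Proportion of Days Covered (PDC) method", at baseline, 3 months and 6 months. It describes the two measures as follows:
- "MMAS-8 is a licensed validated questionnaire to assess medication adherence" (scored 0 to 8).
- "The PDC method utilises pharmacy refill records"; a patient counts as adherent at 80% or more.

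Neither measure is ranked above the other, and there is no rule for what happens if they disagree.

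Section 4.6 compares MMAS scores by t-test or Mann-Whitney and by ordinal logistic regression, with P < 0.05 as the criterion. A chi-square test compares numbers of adherent patients, without saying which measure defines adherence.

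For EQ-5D-5L and SF-36, section 4.4.1.2 says "These tools will be conducted via face-to face or phone interview to assess the health status of respondents". It assigns this to trained research personnel, who also explain the purpose of the study. It does not say whether they are the blinded assessor.

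**The concern.** When the outcome is a questionnaire, the information comes from the respondent. Blinding whoever records the answers stops that person from leading or interpreting them differently by arm. It does not stop a participant who has been given the app from describing their own medicine taking more favourably. Three features of the plan make this relevant:

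- Only the app arm is trained on the app (4.1) and asked to use it to help manage medicines (4.2.1). Both arms then answer an adherence scale again at 3 and 6 months.
- Entry requires an MMAS score below 6 (4.3.1), which leaves room on the scale for reported scores to rise.
- The unblinded pharmacists/researchers screen patients, open the envelopes and give the training. Nothing prevents the same staff from collecting MMAS-8 at follow-up.

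At stake is what a positive result would mean. As written, a significant MMAS-8 difference with no PDC difference could be presented as the primary finding on adherence.

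**Working it through.** **1. Which measures assessor blinding can protect.**

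| Measure | Who supplies the data | What a blinded assessor can do |
|---|---|---|
| MMAS-8 (primary) | Participant, who knows the arm | Limit interviewer bias only |
| PDC (primary) | Refill records | Protect extraction; questionnaire answers cannot move it |
| EQ-5D-5L, SF-36 | Participant, by interview | Limit interviewer bias only |
| Cost questionnaires | Participant | Limit interviewer bias only |
| Clinic measurements | Clinic staff; 4.2 has consultants/researchers collecting at baseline | Unknown: blinded collection at follow-up is not stated |

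MMAS-8 at screening is obtained before the envelope is opened, so knowledge of the arm can affect only the follow-up scores.

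**2. Number of evaluable patients.** The plan's sample-size figures in 4.5 reproduce.

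- Adherence: 2 × (1.96 + 0.84)² × 0.45 × 0.55 / 0.10² = 388.1, stated as 388 per arm; 388 / 0.80 = 485.
- Cost-effectiveness: with W = 28,470, ΔQ = 0.01, SDs 1,000 and 0.01, correlation 0.1 and ΔC = 0.3 × 2,499.15 = 749.7, the variance term is 1,000² + 284.7² − 2 × 0.1 × 1,000 × 284.7 = 1,024,114. Then n = 2 × 2.8² × 1,024,114 / (284.7 − 749.7)² = 74.3, stated as 75 per arm.
- The plan adopts 200 in total. At 20% attrition, 200 × 0.80 / 2 = 80 per arm.

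**3. Chance that a reporting shift alone is declared significant.** The documents give neither an SD for MMAS-8 nor a size for any reporting shift, so both are assumed. The true effect is zero, and the calculation covers one two-sided 5% t-test at one time point. Let SE = SD × √(2/n) and noncentrality = shift / SE. With 158 degrees of freedom the critical value is 1.975.

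| Assumed SD | SE | Smallest significant difference (1.975 × SE) | Shift | Noncentrality | P(significant) |
|---|---|---|---|---|---|
| 1.5 | 0.237 | 0.47 | 0.50 | 2.108 | 0.554 |
| 2.0 | 0.316 | 0.62 | 0.50 | 1.581 | 0.349 |
| 1.5 | 0.237 | 0.47 | 0.25 | 1.054 | 0.182 |
| 2.0 | 0.316 | 0.62 | 0.25 | 0.791 | 0.123 |

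Without a shift the figure is 0.05. With no attrition (100 per arm), the 0.5-point shift gives 0.42 (SD 2.0) to 0.65 (SD 1.5).

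**4. What a PDC condition would do.** Assume PDC has no true difference and is independent of MMAS-8. A rule that PDC need only point the same way is met about half the time, so about half of the false MMAS-8 positives would pass. A rule that PDC must be significant in favour of the app is met 2.5% of the time. In the 0.5-point scenario, the chance of passing both is then 0.554 × 0.025 = 0.014 (SD 1.5) or 0.349 × 0.025 = 0.009 (SD 2.0).

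**5. Separate consequence for QALYs.** Section 4.5 designs for a difference of 0.01 QALY. Take EQ-5D-5L utilities at baseline, 3 and 6 months, the area under the curve over 6 months, and a reporting shift u in one arm:
- shift building linearly to 6 months: u × 0.5 / 2 = 0.25u, so u = 0.01 / 0.25 = 0.04;
- shift complete by 3 months: u × 0.25 / 2 + u × 0.25 = 0.375u, so u = 0.01 / 0.375 = 0.027.

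A utility reporting shift of about 0.03 to 0.04 would therefore equal the whole design difference.

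**The case against.** The strongest reply is that the plan hides nothing. It calls the trial open-label, and the sentence before the blinding claim says "Participants and pharmacists/researchers are unblinded to group assignment and are aware of the intervention". App versus no app cannot readily be blinded, the hypotheses are withheld from participants, and the other primary measure comes from refill records. Much of this stands. A reader might infer that the blinding sentence is false, but the documents support only that it is broader than it can be for self-report. Nor is assessor blinding worthless for questionnaires: a blinded interviewer removes one source of bias.

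Withholding the hypotheses is weak protection, because 4.4.1.2 has staff explain the study purpose and only one arm is trained on the app. How participants are told about the app cannot be seen, since the consent pages are not available, so this remains an inference.

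Three stronger readings are also tempting and not supported:
- EQ-5D-5L and SF-36 do not measure adherence, so a shift in them cannot create a positive adherence result.
- The percentages are not this trial's false-positive rate. They show that a modest shift is enough, not that one will occur.
- PDC is not proof of medicine taking. It measures refills, and section 4.4.2 lists reminding patients to take or refill prescriptions among the app's perceived uses, so refills might rise without more medicine being taken.

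**Conclusion.** The point holds for MMAS-8. It is an unranked co-primary measure, answered by unblinded participants and tested alone at P < 0.05, with no rule for disagreement with PDC. The stated assessor blinding is attached to no measurement and could not remove respondent bias if it were. With no true effect and 80 per arm, an assumed 0.5-point shift is declared significant 35% (SD 2.0) to 55% (SD 1.5) of the time, and a 0.25-point shift 12% to 18%. These figures depend wholly on the assumed SD and shift.

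Self-report in EQ-5D-5L raises a separate issue for the QALYs and the ICER. The remedy is inexpensive, but who collects the questionnaires must be settled before follow-up begins, because it cannot be restored afterwards.

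**What to change.** 1. **Section 4.2.** State that blinding covers the statisticians and the person who extracts PDC or administers the questionnaires, and that MMAS-8, EQ-5D-5L, SF-36 and the cost answers are unblinded self-report. Do not claim blinded clinic measurements unless that is arranged.
2. **Sections 4.2 and 4.4.** Have the blinded assessor already named in 4.2 administer MMAS-8 and the quality-of-life tools at 3 and 6 months, in the same mode in both arms. This should not be the staff who opened the envelope or gave the app training.
3. **Section 4.6.** State that an MMAS-8 difference without a statistically significant PDC difference in favour of the app will be reported as a change in self-reported adherence only. Add that PDC measures refills, which the app may itself prompt.

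The cost is protocol wording and giving questionnaire collection to a role the plan already has. The downsides are a narrower claim if only MMAS-8 moves, and slightly less scheduling flexibility. None of this removes respondent bias; it limits what can be concluded from a result exposed to it.

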4.2.1 Intervention group

- Intervention group will be asked to download and use the CareAide® app to help manage medications for 12 to 24 weeks. CareAide® is a free digital application designed to manage complex medicines schedules and improve adherence.

4.2.2 Control group

- Control group will not be asked to download any digital applications but only receive the usual care by the hospitals.

4.3 Patients' inclusion and exclusion criteria are as follow:

4.3.1 Inclusion criteria:

- Age: 18 years and above
- Diagnosed with selected non-communicable diseases (NCDs): hypertension, diabetes mellitus, heart failure or asthma for at least 6 months
- Prescription generated from one of the following specialty clinics: Medical, Cardiology, Diabetes Mellitus or Asthma clinics
- Medications are prescribed in previous 3 months and refill at the point of recruitment
- Morisky Medication Adherence Scale (MMAS) score < 6
- More than three medications daily or two medications with multiple dosing intervals.
- One or more hospital admissions in the prior 24 months
- Understand and able to command in English and own a smartphone

4.3.2 Exclusion criteria:

- Medications prescribed from other institution providers
- Existing mobile health app or medication reminder app user
- Pregnant
- Cognitively impaired
- Prisoners
- Bed-bound
- Severe diseases/comorbidities – terminal cancer, psychiatry, etc

4.3.3 Withdrawal criteria:

Participants can choose to withdraw at any time for any reason, specified or unspecified, and without prejudice to their care. Participants may be withdrawn if the investigator feels that it is not for the participants' best interest to continue. The following is a list of possible reasons for study intervention discontinuation:

- Screening failure

- Participant withdrawal of consent
- Participant is not compliant with study procedures
- Protocol violation requiring discontinuation
- Lost to follow-up
- Request from sponsor for early termination of study
- Participant death

Withdrawn participants will not be replaced. It will be documented whether or not each subject completes the clinical study. If the Investigator becomes aware of any serious, related adverse events after the subject completes or withdraws from the study, they will be recorded in the source documents and on the Case Report Form (CRF). The Investigator will contact participants who are lost to follow-up. Contacts attempts with such subjects will be documented in the participant's records (e.g., times and dates of attempted phone contact, receipt for mailing a registered letter, etc.).

4.4 Outcome measurements

4.4.1 Phase 1

4.4.1.1 Primary outcome

Medication adherence: CareAide® effectiveness is measured with a medication adherence tool at baseline and follow-up time periods at 3 months and 6 months using Morisky Medication Adherence Scale-8 (MMAS-8) and proportion of days covered (PDC). The primary outcome of the study is medication adherence, which is assessed using the 8-item Morisky Medication Adherence Scale (MMAS-8) and the Proportion of Days Covered (PDC) method. Measurements are taken at baseline and at two additional time points, with a 3-month interval following the intervention. MMAS-8 is a licensed validated questionnaire to assess medication adherence, where a higher score represents higher medication adherence and vice versa. Comprising of 8 items, the score ranges from 0 to 8, where a higher score represents a higher medication adherence. The internal consistency (Cronbach's alpha) of MMAS-8 is 0.83 along with a sensitivity of 93% and a specificity of 57%. The PDC method utilises pharmacy refill records (Raebel et al., 2013). The PDC can be calculated as below (Hess et al., 2006; Raebel et al., 2013; Pednekar et al., 2019):

$Nm/Nd \times 100\%$

Where N_m denotes the number of days covered by the medication while N_d meant the number of days in the study period. The patients are considered to be adherent if their PDC scores are ≥ 0.8 or 80% (Karve et al., 2009). The prescription refill data was extracted from outpatient/hospital database.

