4.5 Sample Size

The primary outcome for this study is to assess medication adherence of patient after using mobile health application. Therefore, sample size for this randomized controlled trial is calculated using the continuous outcome formula below (Charan & Biswas, 2013; Wittes, 2002):

$$n_i = \frac{2(Z_{\alpha/2} + Z_{\beta})^2 P (1 - P)}{(P_1 - P_2)^2}$$

n_i = sample size required for each group ($i = 1,2$)

$Z_{\alpha/2}$ = Assumed type I error: α equal to 5%, then $Z_{0.05/2} = Z_{0.025} = 1.96$ (From Z table)

Z_{β} = Assumed power of 80% $Z_{\beta}=0.84$

$P_1 - P_2$ = Effect Size= Difference in the proportion of events in two groups

P = Total prevalence

Total Sample size needed: 388 per group

Note: Based on few past studies reported for non-adherence rate for patients in Malaysia is within 46.6% to 56% (Ting et al., 2019). Therefore, assumption of prevalence of chronic disease is 70%

of the adult and adherence rate of 50% is made. A systematic review showed that mobile app able to improve adherence by 7% to 40% (Pérez-Jover et al., 2019). Medication non-adherence rate of 50% is expected in control group and 40% is expected in intervention group. For a 10% absolute difference in medication non-adherence rate between control and intervention group, 388 patients per arm should be recruited in the study assuming a type I error of 5% and power of 80%.

N (number to enrol) * (1-% drop out) = desired sample size

Therefore N (number to enrol) = desired sample size / (1- % drop out)

$N = 388 / 0.80 = 485$ per group

Based on a systemic review published by Wood and colleagues found out there is a possibility of 20% loss of follow-up, drop out and those who are unable to meet the inclusion criteria (Wood et al., 2004). Therefore, a minimum sample size of 970 is needed in this study, with the number of 485 in each arm.

The sample size obtained from the primary outcome is too large and which might need to spend more time and manpower. Hence, the sample size calculation is repeated with the use of secondary outcome which is cost-effectiveness economic evaluation of the study. Glick (2011) formula is applied for the calculation of sample size as it incorporates all important economic evaluation informations such as difference in treatment costs and effects and willingness to pay threshold in a single formula.

$$n_i = \frac{2 \left(Z_{\alpha/2} + Z_{\beta} \right)^2 \left(Sd_c^2 + (W^2 Sd_Q^2) - (2 W p Sd_c Sd_Q) \right)}{(W\Delta Q - \Delta C)^2}$$

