4.6 Data Analyses

Intention to treat (ITT) analysis will be applied to evaluate the results to avoid any bias. The data analysis will be using the SPSS version 27. Data will be coded and analysed. Descriptive or categorical data will be expressed as mean \pm standard deviation (SD) unless otherwise stated. Student t-test will be used for analysis of normally distributed or continuous variables. Mann-Whitney test will be used for non-normally distributed data. Categorical data will be analysed using Chi-square or Fischer's exact test. A value of $P < 0.05$ is considered statistically significant.

The prevalence of medication compliant is quantified at 3 months and 6 months follow-up. Independent t-test or Mann-Whitney test will be used to compare MMAS score rankings between the intervention and control groups. Chi-Square test of independence will be used to determine the difference in number of patients with medication adherence between the intervention and control groups at 3 months and 6 months follow-up. Ordinal logistic regression, with the MMAS adherence score ranking, will be used to examine the association between intervention and control groups.

For the perception and satisfaction towards the app, the frequency and percentage of respondents in each category (strongly disagree to strongly agree) will be calculated. The median of each statement will then be calculated to give an overview of perception and satisfaction towards the CareAide® app. Chi-square, Mann-Whitney U, Kruskal Wallis, Chi-square tests and logistic regression will be used where appropriate. The open-ended question will be analysed using thematic analysis as proposed by Braun and Clarke (2012). Codes will be assigned to the data to describe the content. After the coding is completed, themes will be generated, reviewed, and named. Linear regression analysis will be conducted to determine the independent predictors of HRQoL.

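### Adherence has two unranked instruments, two unranked visits and several unadjusted tests as its primary outcome, with no rule for what counts as success

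*Combined protocol and SAP*

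**What the plan says.** Section 4.4.1.1 states that adherence is "assessed using the 8-item Morisky Medication Adherence Scale (MMAS-8) and the Proportion of Days Covered (PDC) method", measured at baseline and at 3 and 6 months. It ranks neither the two instruments nor the two follow-up visits. It gives one outcome cut-off: "The patients are considered to be adherent if their PDC scores are" at least 0.8, or 80%. For MMAS-8 it gives a 0 to 8 range but no outcome cut-off. The MMAS score below 6 in section 4.3.1 is an entry criterion.

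Section 4.6 lists three analyses:

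- "Independent t-test or Mann-Whitney test will be used to compare MMAS score rankings between the intervention and control groups". No visit is given.
- A chi-square test for the "difference in number of patients with medication adherence between the intervention and control groups at 3 months and 6 months follow-up". No instrument is named.
- "Ordinal logistic regression, with the MMAS adherence score ranking, will be used to examine the association between intervention and control groups". No visit is given.

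The only decision threshold is that P below 0.05 "is considered statistically significant", and it applies to each test separately.

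The adherence calculation in section 4.5 is for a single comparison of proportions: "Medication non-adherence rate of 50% is expected in control group and 40% is expected in intervention group". It concludes that "388 patients per arm should be recruited in the study assuming a type I error of 5% and power of 80" per cent. It names no instrument and no visit. Section 4.5 then calls the resulting size too large and adopts 200 patients in total, sized on the cost-effectiveness outcome.

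**The concern.** A reader of the final report should be able to tell in advance which single result, or which combination, answers the primary question. This plan does not allow that. MMAS-8 is a questionnaire answered by participants who know their group, and PDC comes from refill records, so the two could diverge. So could the 3-month and 6-month results. Nothing says which one decides.

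Several unranked results at an unadjusted 5% also leave room to base the claim on whichever is positive. Section 4.5 assumes 5% type I error for one comparison, and nothing in section 4.6 limits the trial's adherence conclusion to one comparison.

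**Working it through.** **1. The plan's own figure.** Inputs from section 4.5: 50% against 40% non-adherent, two-sided 5% (z = 1.96), power 80% (z = 0.84). With P = (0.50 + 0.40)/2 = 0.45:

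n = 2(1.96 + 0.84)² × 0.45 × 0.55 / 0.10² = 2 × 7.84 × 0.2475 / 0.01 = 388.08.

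This reproduces 388 per arm, and 388/0.80 = 485. The figure belongs to one test of two proportions at 5%.

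**2. What section 4.6 provides instead.** The chi-square is placed at two visits, which already makes two results. The MMAS score test adds one, or two if it is run at both visits, a schedule the text does not state. The ordinal regression largely repeats the MMAS score test and is not counted separately below.

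**3. False-positive chance if any one result suffices.** With no true effect and m tests:

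chance = 1 − P(|Z₁| ≤ 1.96, …, |Zₘ| ≤ 1.96).

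For independent tests this is 1 − 0.95ᵐ: 9.75% for m = 2 and 18.5% for m = 4. Adherence tests on the same patients are correlated, so the true values are lower. The documents give no correlations. I assumed 0.5–0.8 between visits, 0–0.7 between instruments, and the product of the two across both. I then checked the result by simulation: 20,000 null trials per setting, 80 per arm (200/2 less 20%), 50% adherent.

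| Results that may count | Normal approximation | Simulation |
|---|---|---|
| Chi-square on PDC, 3 and 6 months | 7.8–9.1% | 8.1–9.4% |
| plus one MMAS test | 10.8–13.6% | 12.1–13.8% |
| plus MMAS at both visits | 12.8–17.3% | 14.3–17.4% |

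A false positive in the app's favour is about half as likely: roughly 4–5%, 5–7% and 6–9%, against a nominal 2.5%.

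**4. Two variations.**

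- *Chi-square on an MMAS cut-off rather than PDC.* The tests then overlap more. In simulation the second and third rows become 10.5–11.7% and 12.1–14.1%.
- *Cumulative PDC.* If 6-month PDC covers all six months, it contains the 3-month window. With equal variances and correlation r between the two periods, the visit correlation is √((1 + r)/2), which is 0.87 for r = 0.5 and 0.95 for r = 0.8. The first row then falls to about 6.5–7.3% if this correlation applies to the test statistics, or about 7.4–8.5% if it applies to PDC before the cut at 80%.

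**5. The opposite rule.** If both instruments had to be significant at 6 months, the false-positive chance would be 0.2–1.7% (normal approximation) or 0.3–1.3% (simulation). There is no inflation.

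**6. Holm across the two instruments at one visit.** The simulated false-positive chance is 4.3–4.6%, so the 5% level is held.

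**The case against.** **No passage says that one positive result is enough.** This is correct, and it limits the point. A reader might infer that the trial has a type I error of, say, 15%. The documents do not support that. They establish that the decision rule is missing, and step 5 shows that a both-must-succeed rule would be conservative. What remains is that the any-one-wins reading is not excluded either.

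**Section 4.5 already points to a primary test.** A comparison of proportions does suggest the chi-square. But section 4.5 names no instrument or visit, section 4.6 places that test at two visits, and neither section calls it primary. A reader might also take the 5% in section 4.5 as the error rate on which the enrolled trial rests. That calculation is set aside, because the 200 patients come from the cost-effectiveness calculation.

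**The chi-square must be on PDC.** This is the natural reading, since PDC has the only outcome cut-off, but it remains an inference. The sentence names no instrument and sits between two MMAS sentences. If it means MMAS, the inflation is smaller, and PDC is covered only by the general test list in section 4.6.

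**The percentages rest on assumed correlations.** They do. The direction is firm, because unless the tests are perfectly correlated, more than one unadjusted 5% test gives more than 5%. The exact sizes are illustrative.

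**Conclusion.** The point stands as a missing primary specification. Adherence by two instruments at two visits is primary and is tested several ways at an unadjusted 5%, with no ranking, success rule or multiplicity control. This follows from the text and needs no assumption.

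The size is conditional on an any-one-wins reading and on the assumed correlations. It is about 8–9% for two chi-squares (6.5–8.5% with cumulative PDC), 11–14% with one MMAS test added and 13–17% with MMAS at both visits. The last two become about 10–12% and 12–14% if the chi-square uses an MMAS cut-off. Under a rule that both instruments must succeed at one visit, the figure is below 2%. The gap should be closed before outcome data are seen.

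**What to change.** In sections 4.4.1.1 and 4.6, before outcome data are seen:

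1. Name one primary comparison: one instrument, one visit, one test. Label every other adherence analysis secondary or supportive. A proportion adherent compared by chi-square fits the form of the calculation in section 4.5, and PDC of at least 80% is the only outcome cut-off already defined. The choice of instrument is the sponsor's.
2. If both instruments stay primary, apply Holm across the two at one named visit.
3. State the instrument and cut-off for the chi-square, and the visit for each MMAS analysis.

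The cost of a single primary comparison is wording only. The 388 calculation is unaffected, and the sponsor gives up the option to claim success on whichever result is positive.

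Holm costs power for each instrument. At 80 per arm, the test of 50% against 40% has z = (0.10 − 1.96√(2 × 0.45 × 0.55/80)) / √((0.25 + 0.24)/80) = −0.69, which is about 24% power. Under Holm this falls to about 18–19%. The MMAS test falls from about 36% to 27–28%, assuming a normally distributed score and a shift of about 0.25 SD, neither of which is in the documents.
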